Correcting Asthma Symptom Over-perception: As part of the intervention, participants will receive an AM2 device. Before each daily PEF measurement, they will be instructed to guess their PEF with no advantage for guessing too high vs. too low. After the maneuver, participants will be able to view, in the display of the AM2 device, their PEF values and will be instructed to compare their results with their pre-effort estimated values. Similar PEF feedback training strategies have been shown to be effective in children with asthma.⁸⁷ We will also explain to the consequences of over-perception (e.g., over-use of β -2 agonists) and links with asthma and medication beliefs, and SMB. This approach is consistent with adaptive perspective taking and cognitive restructuring, which are taught in the 3RP. In addition, we will provide psychoeducation on anxiety sensitivity (if linked to over-perception) using mindfulness skills and relaxation training, which are taught in the 3RP, and shown to be effective in patients with PTSD.^{236,237}

Integrating Asthma SMB into 3RP: To guide design of the SMB support components of

 Mount Sinai	Protocol Title:	Assessing Inflammatory and Behavioral Pathways Linking PTSD to Increased Asthma Morbidity in WTC Workers
	Principal Investigator Name/Contact Info:	[name], DrPH [contact]; [contact]
	Primary Contact Name/Contact Info	[name], MS [contact]; [contact]
	Date Revised:	07/25/16
	Study Number:	IF# 1896970; GCO# 16-0945

the intervention, we will apply the SRM, which has been used to build coping strategies, knowledge, and skills in patients with low adherence to self-management tasks by addressing beliefs that influence SMB.¹²⁷ Illness and medication beliefs having the strongest associations with SMB will be addressed in the intervention. Cognitive restructuring and adaptive perspective taking methods will be incorporated into the 3RP sessions to address misconceptions about asthma in WTC workers with PTSD. For example, patients may feel that WTC-related asthma cannot be controlled or that arousal symptoms resulting from PTSD are specific to asthma. These views can be “reconstructed” by teaching patients about the effective management of asthma and how to differentiate PTSD and anxiety symptoms from asthma symptoms. In addition, according to the SRM, patients interpret symptoms in relation to their mental model of illness and these assessments in turn guide their SMB. Appraisal of the efficacy of their actions reinforces or modifies SMB. Thus, we will work on helping WTC workers develop accurate perceptual discrimination of symptoms arising from asthma, thereby creating a process in which they search for the appropriate signals to initiate and appraise the effects of self-management thus, generating effective self-regulatory feedback controls. We will also address avoidance behaviors – specifically, avoidance of asthma SMB because of their association with the WTC disaster (i.e., trauma-cues). Mindful awareness training included in the 3RP will focus specifically on reducing these avoidance behaviors.

Refinement of New Components: We will conduct qualitative interviews with ~10 participants who completed the 12-month interview to evaluate and refine the new 3RP components. During the audio-recorded sessions, we will share the educational messages and counselling strategies and ask participants to provide feedback.²³⁸

Training and Fidelity: Masters-level clinicians will be trained to deliver the adapted 3RP intervention by [name]. [name] will provide weekly supervision and review audio-taped sessions for treatment fidelity. Pilot RCT Procedures: [name] will adapt the 3RP procedural manual to incorporate new components. We will use data from the 12-month interview to identify WTC workers with asthma and PTSD for the pilot (N=60). Eligible WTC workers who agree to participate will be randomized 1:1 (using adaptive randomization to balance the number of participants in each arm with respect to age, sex and PTSD symptoms severity) to the intervention vs. an attention control group.

Intervention Group: Participants randomized to the adapted 3RP condition will participate in the manualized 8-session group -based program (4-8 participants per group). They will also receive an unblinded AM2 device during the first 6 weeks of the intervention. Attention Control: Control patients will participate in an 8-session group-based program of similar time and therapist attention. The control intervention will consist of educational sessions covering general asthma knowledge (Asthma 1-2-3)²³⁹ group-based support. They will receive blinded AM2 devices.

Outcome Assessment: A telephone follow-up survey 4 weeks after the last session will be administered to assess the patient’s illness and medication beliefs, anxiety sensitivity, their adherence to asthma SMB, and PTSD symptoms. Data Analysis: 1) Quantitative Assessment: Differences in illness (B-IPQ), medication beliefs (BMQ), anxiety sensitivity (ASI-3), adherence to asthma medications (MARS), and PTSD symptoms (PCL) will be assessed using a t-test

 Mount Sinai	Protocol Title:	Assessing Inflammatory and Behavioral Pathways Linking PTSD to Increased Asthma Morbidity in WTC Workers
	Principal Investigator Name/Contact Info:	[name], DrPH [contact]; [contact]
	Primary Contact Name/Contact Info	[name], MS [contact]; [contact]
	Date Revised:	07/25/16
	Study Number:	IF# 1896970; GCO# 16-0945

or Wilcoxon test, as appropriate. 2) Qualitative Feedback: The post-intervention interview will also include open-ended questions for: a) recollection of specific messages from the counseling, b) satisfaction and perceived usefulness, and c) ways of improving the messages and their delivery. Power: The study will have >80% power to identify a clinically meaningful differences in IPQ, BMQ, ASI, MARS, and PCL scores for 30 patients in each study arm (n=60).

i) Provisions to Monitor the Data to Ensure the Safety of subjects

Data Safety and Monitoring Plan

We have established a monitoring plan for the observational phase of the study (Aims 1-3).

Overview

- A. Brief description of the purpose of the study: The goal of the proposed study is to examine the inflammatory and behavioral mechanisms underlying the association between PTSD and increased asthma morbidity among WTC rescue and recovery workers.
- B. Adherence statement: The Data Safety Monitoring Plan (DSMP) outlined below for the proposed study will adhere to the protocol approved by the MSH and Queens College IRBs.
- C. Data quality and management: Principal investigators will review all data collection forms on an annual basis for completeness and accuracy of the data as well as protocol compliance. A statement reflecting the results of the review will be sent to the NIOSH in the annual report.

Adverse Events

- A. Adverse event grading
 1. Attribution scale: An adverse event is defined as both an expected side effect that is of a serious nature, or an unexpected side effect/event regardless of severity. All events will be graded as to their attribution (unrelated to protocol, or possibly, probably, or definitely related to protocol). Any event that is reported to either a principal investigator or their designated research associates by the subject or medical staff caring for the subject and which meets the criteria will be documented as such.
 2. Expected risks: As detailed in the consent form, the expected risks include:
 - Discomfort caused by personal questions asked in the survey.
 - Distress resulting from the questions related to PTSD or depressive symptoms.
 - Complications of the breathing test which may include dizziness or light-headedness due to deep respirations.

	Protocol Title:	Assessing Inflammatory and Behavioral Pathways Linking PTSD to Increased Asthma Morbidity in WTC Workers
	Principal Investigator Name/Contact Info:	[name], DrPH [contact]; [contact]

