Potential participants with a diagnosis of asthma will be identified from the WTCHP database and our prior WTC cohort study (HSM#12-00422; consent included language authorizing contact for future studies). The research team will send out a letter from the study's PI, [name], or an investigator who is a practicing physician at the WTCHP sites. Participants will have 1 week to respond to the letter. If the research team does not hear back from the participant after 1 week, then we will call the participant to offer participation in the study. WTC workers who agree to

 Mount Sinai	Protocol Title:	Assessing Inflammatory and Behavioral Pathways Linking PTSD to Increased Asthma Morbidity in WTC Workers
	Principal Investigator Name/Contact Info:	[name], DrPH [contact]; [contact]
	Primary Contact Name/Contact Info	[name], MS [contact]; [contact]
	Date Revised:	07/25/16
	Study Number:	IF# 1896970; GCO# 16-0945

participate will be contacted by a research assistant (RA) who will explain the study and schedule an in-person assessment.

b) Inclusion and Exclusion Criteria

Inclusion Criteria: Participants will be ≥ 18 years of age, have a diagnosis of asthma made by a health care provider, and speak English or Spanish. Exclusion Criteria: WTC workers will be excluded if they have chronic obstructive lung disease (COPD) or other chronic respiratory illness. Additionally, individuals with a history of heavy smoking (≥ 15 pack-years) will be excluded because of the possibility of undiagnosed COPD. Current smokers will be included in the study if their cumulative smoking history does not exceed this threshold.

c) Number of Subjects

A total of 400 patients will be enrolled over a 3-year period and followed for 1 year. At the ISMMS site, we will recruit 300 patients. At the Queens College site we will recruit 100 patients.

d) Study Timelines

The study will take place from September 1, 2016 to August 31, 2021. Participants will be followed for 12 months with in-person interviews at baseline, 1 month, 6 months and 12 months.

Table 5. Study Timeline

TASK	Yr 1	Yr 2	Yr 3	Yr 4	Yr 5
Study Preparation	■				
Baseline interviews		■	■	■	
Follow-up interviews		■	■	■	
Data Analysis		■	■	■	
Pilot RCT				■	
Dissemination			■	■	■

e) Study Endpoints

N/A

f) Procedures Involved in the Human Research

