Sociodemographics	Age, sex, race/ethnicity, language, health literacy	NHIS, NVS ²¹³	✓					

PEF: peak expiratory flow, NAS: National Asthma Study, NAEPP, EHR: electronic health record, PTSD: posttraumatic stress disorder, SCID: Structured Clinical Interview, PHQ-9: Patient Health Questionnaire, NHIS: National Health Interview Survey, NVS: New Vital Sign

Outcome Measures (Appendix A and Table 3): A. Systemic and Airway Inflammatory

Markers: Peripheral Pro-inflammatory Cytokines: To measure peripheral cytokine, blood will be collected at baseline, 1-, 6, and 12-months, in the morning (8-9 AM, prior to eating) to decrease potential confounding factors of diurnal variation and diet,⁷ using methods employed by members of our research team.¹⁷⁶ Samples will be processed with 30 minutes of collection by centrifugation and separation of plasma into aliquoted samples stored at -80°C. Plasma cytokine levels will be analyzed using a multiplex assay (Milliplex Human Th17 Magnetic Bead, Eotaxin and IL-8, Billerica, MA, USA) as in our prior studies.¹⁷⁷ Briefly, samples, standards, and controls will be added to the appropriate wells. The premixed magnetic beads will be added to each well and incubated on a plate shaker for 18 hours at 4°C. After washing, detection antibody will be added and incubated on a plate shaker for 1 hour, followed by Streptavidin-

	Protocol Title:	Assessing Inflammatory and Behavioral Pathways Linking PTSD to Increased Asthma Morbidity in WTC Workers
	Principal Investigator Name/Contact Info:	[name], DrPH [contact]; [contact]
	Primary Contact Name/Contact Info	[name], MS [contact]; [contact]
	Date Revised:	07/25/16
	Study Number:	IF# 1896970; GCO# 16-0945

Phycoerythrin for 30 minutes. The plate will be run on the Luminex 200 system (Luminex Corp., Austin, TX) and data will be analyzed using the MILLIPLEX Analyst Software (EMD Millipore Corp., Billerica, MA).

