Sputum Inflammatory Markers: To limit participant burden, we will only perform sputum induction at the 1-month visit. However, we will have repeated measures of systemic cytokines, which will allow for longitudinal assessment of the association of PTSD-related inflammation and asthma control. During the baseline visit, we will collect data on ICS use and monitor adherence for 4 weeks. Using this information, we will be able to control for the potential effect of ICS and sputum inflammatory markers. Sputum will be collected on 175 participants (see power calculation) following standardized protocols.^{178,179} Briefly, subjects will be pre-treated with 360 µg of albuterol followed by spirometry to ensure an FEV₁ ≥60% predicted. They will then undergo a 12-minute sputum induction with PEF monitoring for participant safety. Subjects will be excluded from sputum induction if: 1) their FEV₁ <60% predicted (for safety reasons), 2) they had a respiratory tract infection <4 weeks prior to sputum induction, or 3) an asthma exacerbation or oral corticosteroid use <4 weeks prior to sputum induction. We will weight sputum samples, add a dithiothreitol (DTT) containing Sputolysin Reagent (Calbiochem, San Diego, CA, USA; 1 ml to 1 gram of sample), and then will place samples in a 37°C shaker for 15 minutes. The sample will be washed with PBS and spun down; the supernatant will be stored at -80°C.

Sputum Cell Differential: Cytospins will be prepared and stained with Diff-Quick (Dade Diagnostics of PR, Aguada, PR) for differential cell counts. The sputum cell differential will be determined by counting ~500 white blood cells on cytocentrifuge slides, excluding samples with a cell viability <50% and >20% squamous cells.^{178,180} Sputum eosinophilia will be defined as >2%;¹⁸¹⁻¹⁸³ sputum neutrophilia as ≥40%.¹⁸⁰ **Sputum Cytokines:** Sputum supernatant will be analyzed for a panel of cytokines using the multiplex assay as described above.

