generalized linear model to assess the association of PTSD with sputum eosinophilia or neutrophilia (logit link), or cytokine levels (identity link) after controlling for possible confounders such as age, sex, race/ethnicity, ICS dose (calculated after adjusting for adherence), asthma onset in relation to WTC exposure, BMI, comorbidities, and depression. We will calculate the false discovery rate from the p-values to control for testing of multiple cytokines.²²³ Then, we will assess the unadjusted association of plasma and sputum cytokine levels as well as the associations of airway eosinophilia, neutrophilia, and cytokines levels with measures of asthma control using correlation coefficients or Wilcoxon test. The adjusted relationship of inflammatory markers (systemic and sputum) and asthma control measures over time will be assessed using generalized estimating equation (GEE) models (logit or identity link and autoregressive correlation structure for repeated measures over time). The model will include an interaction between inflammation markers (e.g., neutrophilia, etc.) and PTSD status to assess for potential effect modification (i.e., differential effect in subjects with vs. without PTSD). Finally, we will fit a fixed effects model (i.e. limited to within subject variability) to assess the longitudinal effect of changes in systemic cytokines levels on asthma morbidity makers.

We will use structural equation modeling (SEM; see details below) to test whether systemic inflammation, leading to airway neutrophilia and high IL-6 levels, mediates the association between PTSD and increased asthma morbidity. Following the MacArthur approach²²⁴ for assessing mediation, main effects as well as interactions between PTSD and inflammatory markers will be included as predictors of asthma morbidity.^{225,226} The analyses described above will establish if PTSD has a significant effect on the mediators (i.e., inflammatory markers), which is the first step of mediation. What is then needed is to also show that these factors are also associated with asthma morbidity measures while controlling for PTSD. Building a SEM including inflammatory markers, PTSD and an interaction variable of PTSD with the potential mediators, while controlling for other confounders, will provide a formal test of mediation.

Table 3. Power Calculations for Aim 1

Outcome	Proportion/ Mean among Participants without PTSD	Δ Proportion/ Mean for Participants with PTSD	Sample Size for 80% Power

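### Recent respiratory infection is not recorded at most plasma cytokine draws, so acute illness can distort the within-person cytokine–asthma association in Aim 1; size and net direction are unknown

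*Combined protocol and SAP*

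**What the plan says.** Section f (Procedures), under the systemic and airway markers, schedules four plasma draws: "blood will be collected at baseline, 1-, 6, and 12-months, in the morning (8-9 AM, prior to eating". The stated purpose of the timing and fasting rule is "to decrease potential confounding factors of diurnal variation and diet". No condition on recent illness or systemic steroids is given for blood.

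The next part of section f, on sputum, does have one. People are excluded from sputum induction if "they had a respiratory tract infection <4 weeks prior to sputum induction, or 3) an asthma exacerbation or oral corticosteroid use <4 weeks" before it. Sputum is taken once, at month 1, in 175 participants. The safety remark there is attached only to the FEV1 criterion; no reason is given for the 4-week criteria.

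Because sputum is taken once, the plan puts the longitudinal part of Aim 1 on blood: "we will have repeated measures of systemic cytokines, which will allow for longitudinal assessment". In section h (Data Analyses, Aim 1) the repeated cytokines enter GEE models of asthma control. A further model takes morbidity as its outcome: "we will fit a fixed effects model (i.e. limited to within subject variability) to assess the longitudinal effect of changes in systemic cytokines levels". The example confounders, listed with the cross-sectional model, are "age, sex, race/ethnicity, ICS dose (calculated after adjusting for adherence), asthma onset in relation to WTC exposure, BMI, comorbidities, and depression".

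The study-level exclusions in section b do not help. They concern chronic disease ("WTC workers will be excluded if they have chronic obstructive lung disease (COPD) or other chronic respiratory illness") and heavy smoking, not acute illness.

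**The concern.** Plasma and the Asthma Control Questionnaire (ACQ) are collected at the same visits. A respiratory infection in the preceding weeks could raise a cytokine such as IL-6 and worsen asthma control together. A fixed-effects model removes stable differences between people. It does not remove something that comes and goes between visits and moves both variables. GEE does not remove it either unless it is a covariate.

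None of the named confounders carries this information. Age at entry, sex, race/ethnicity and asthma onset are fixed within a person. Comorbidities mean the Charlson Index, scheduled at baseline only, and physician-diagnosed chronic conditions. ICS dose, BMI and depression do not record infection or systemic steroid use.

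At stake is how a within-person result is read. A positive slope would be taken as evidence for a systemic-inflammation pathway when part of it could reflect intercurrent illness. A null or negative slope could be affected too, if steroid courses act in the opposite direction.

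**Working it through.** The plan gives no figure for the within-person analysis, so there is none to reproduce. The check has two parts.

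**1. Coverage of the screen.** Planned draws: 400 × 4 = 1,600. The sputum screen reaches 175 people at one visit, which is 175 / 1,600 = 10.9% of draws. It also governs sputum only: a person screened out at month 1 still has blood taken. The other 400 − 175 = 225 participants, and every draw at months 0, 6 and 12, have no stated screen.

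**2. Size under assumptions.**

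From the documents:
- 400 enrolled and 80% retention, so 320 people × 4 draws, with 320 × 3 = 960 within-person degrees of freedom.
- IL-6 given as 4 (2) pg/ml in the Aim 1 power table, read as mean and SD, so variance 4.

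Assumed:
- Half of that variance is within person: 2, SD 1.41 pg/ml. The table does not say whether its IL-6 is plasma or sputum.
- Within-person ACQ SD 0.5, variance 0.25.
- Illness present at a share q of draws, adding a pg/ml to IL-6 and b points to ACQ.
- True cytokine effect zero; two-sided test at 0.05.

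Formulas:
- Within-person variance of IL-6: V = 2 + q(1−q)a²
- Spurious slope: s = q(1−q)ab / V
- Residual variance: R = 0.25 + q(1−q)b² − s²V
- Standard error: √(R / (960 V))
- False-positive rate: chance that a normal variable with mean s/SE and SD 1 lies outside ±1.96

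Example, q = 5%, a = 1, b = 0.5: q(1−q) = 0.0475; V = 2.0475; s = 0.02375 / 2.0475 = 0.0116; R = 0.25 + 0.0119 − 0.0003 = 0.2616; SE = √(0.2616 / 1,965.6) = 0.0115; s/SE = 1.0; false-positive rate about 17%.

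| Share of draws | IL-6 shift (pg/ml) | ACQ shift | Slope (ACQ per pg/ml) | False positives, formula | False positives, simulation |
|---|---|---|---|---|---|
| 5% | +0.5 | +0.25 | 0.003 | 6% | 6% |
| 2% | +1 | +0.5 | 0.005 | 7% | 7.5% |
| 5% | +1 | +0.5 | 0.012 | 17% | 18% |
| 10% | +1 | +0.5 | 0.022 | 46% | 46% |
| 10% | +2 | +0.5 | 0.038 | 94% | 93% |

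The simulations fitted the fixed-effects model itself. Adding a visit-level illness indicator returned the false-positive rate to about 5% in every setting, assuming illness is recorded without error.

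Scale of the largest slope: 0.038 × 2 pg/ml (the PTSD difference in the power table) = 0.08 ACQ points.

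Direction: if oral steroid courses lower cytokines while marking poor control (an assumption), they push the slope the other way. An equally frequent, equal and opposite steroid effect brought false positives back to about 5–6% at both 5% and 10% of draws with a shift of 1 pg/ml.

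**The case against.** Every illness input is assumed. The documents support no particular row of the table, and with rare or mild illness the problem nearly vanishes. The slopes are small even in the worst row, so a high rejection rate overstates the practical consequence. The confounder list is introduced as examples, so an illness term is not ruled out. Asthma medications are recorded at each visit and acute visits are captured by self-report and electronic data, so steroid courses and treated exacerbations could be partly reconstructed. The fixed-effects model closes Aim 1, and H1a to H1c do not specify a within-person test.

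Most of this stands, and it limits the point to an inexpensive improvement. It does not remove it. An open confounder list is no use for a variable that is not collected, and recent infection appears nowhere outside the sputum exclusion. Infection history not asked at the draw is hard to recover later.

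A reader might infer three stronger things that the documents do not support:
- That a positive within-person result would probably be an artefact. The 93% figure belongs to one assumed setting, and the net direction is unknown.
- That the H1a comparison of people with and without PTSD is undermined to the same degree. That cross-sectional contrast is much less affected.
- That draws with recent steroid use or exacerbation should be left out of the primary analysis, as for sputum. Both are partly consequences of poor control, so excluding them selects on the outcome.

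**Conclusion.** The point holds as a gap in data collection and adjustment. The screen used for sputum is not applied to plasma, recent infection is not recorded at most draws, and the longitudinal Aim 1 models therefore cannot separate intercurrent illness from the cytokine–asthma association they are meant to estimate.

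Under the assumptions above, false positives run from about 6–8% to about 93%, with slopes of about 0.003 to 0.04 ACQ points per pg/ml. These are illustrations: illness frequency, the shifts and both within-person SDs are not in the documents. They show that the association can be distorted, not that it will be, nor in which direction overall.

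**What to change.** 1. Ask the three sputum screening items (respiratory infection, exacerbation and oral corticosteroid use in the past 4 weeks) at every blood draw, months 0, 1, 6 and 12.
2. Enter recent infection as a time-varying covariate in the Aim 1 longitudinal plasma-cytokine models (GEE and fixed effects).
3. Handle oral steroid use and exacerbation only in sensitivity analyses, by adjustment or exclusion.
4. Report the unadjusted all-draws result alongside.

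Cost: a few questions per visit, already written for sputum; the medication review at each visit can support the steroid item. The infection item relies on self-report, so adjustment will be incomplete where recall is poor. The extra covariate costs a little precision.
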